6.9 Appendix 9: Criteria for potentially clinically significant values of safety endpoints

No lab data are recorded during the study.

Vital signs are captured only during the Day 1.

Thus, no criteria to flag potentially clinically significant changes in the laboratory or vital sign values can be applied.

6.10 Appendix 10: Compliance

The number of patients with doses missed (as derived by the total days of treatment duration [Date of last dose – Date of first dose +1 minus the ZLP-AI kits with complete dose delivery]) will be summarized via the number and percent of study participants meeting the following criteria in order to assess treatment compliance:

- Participants missing 1 dose
- Participants missing 2 doses
- Participants missing 3 doses
- Participants missing ≥ 4 doses

Additional evaluation of treatment compliance will be measured as follows:

For each participant the percentage of used ZLP-AIs with complete dose delivery relative to the expected treatment duration will be calculated. The overall treatment compliance will be summarized descriptively.

Participant's Compliance: [number of used and returned ZLP-AIs with complete dose delivery / (Expected duration of use)]

The expected treatment duration for each participant will be calculated as: (date of last scheduled visit / EW visit) - (date of first ZIL-AI use) +1.

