**Table 1-1: Schedule of study assessments**

Period	Screening Period	Treatment Period								EW b (In-clinic)	SFU Visit c (Phone call)
Name	Screening (In-clinic)	Day 1 (In-clinic)	Day 2 (Phone call) a	Day 4 (Phone call) a	Day 6 (Phone call) a	Day 8 (Phone call) a	Day 10 (Phone call) a	Day 12 (Phone call) a	Day 14 (In-clinic)		
Visit #	1		2	3	4	5	6	7	8	9	
Day	1		2	4	6	8	10	12	14	(Final dose +7±3 days)	
Participant completes postinjection SIAQ (SIAQ POST module) j		X							X		
Study personnel collect ZLP-AI devices from each participant to send to UCB for structural/mechanical integrity assessment t m		X							X		
Drug and device accountability									X		
Record TEAEs, SAEs, ADEs, SAEs, medication errors, ISR, and device deficiencies n		X	X	X	X	X	X	X	X	X	
Blood sampling for ZLP plasma concentrations o	CCI										

ADE=adverse device effect; AE=adverse event; AI=auto-injector; βHCG=beta human chorionic gonadotropin; C-SSRS=Columbia-Suicide Severity Rating Scale; EW=early withdrawal; IMP=investigational medicinal product; ISR=injection site reaction; IXRS=interactive response technology;

MGFA=Myasthenia Gravis Foundation of America; PK=pharmacokinetic; SAE=serious adverse device event; SAE=serious adverse event; SFU=Safety

Follow-Up; SIAQ=Self-Injection Assessment Questionnaire; ZLP=zilucoplan

a Telephone visits which would be scheduled to occur on a weekend day may be skipped, and the data for the respective days (Saturday and Sunday) will be collected on the next clinic business day (Monday).

b If a study participant permanently withdraws from the study, the study participant should return to the clinic for an EW Visit as soon as possible but no later than the next scheduled in-clinic visit.

c Study participant will be required to perform a SFU telephone call 7 days (±3 days) after their final study dose of ZLP using the ZLP-AI.

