4.2.1 Definition of endpoint(s)

The primary estimand is defined in [Table 1–1](#) based on the Treatment Policy definition, regardless of intercurrent events.

The primary variable is the Effective self-administrations of zilucoplan using the ZLP-AI as captured in the study eCRF based on the investigator's opinion.

The Effective self-administration is defined as:

- Complete dose delivery: completeness of the delivery as confirmed by the Investigator. The entire dose of IMP should be completely delivered (ie, the yellow plunger that can be seen through the device window should be completely depressed).

Thus, the investigator should answer the following eCRF question for each ZLP-AI used and returned throughout the Intervention Period:

“Did the study participant self-inject the complete dose Zilucoplan (confirmed by visual inspection of the device window by the investigator, showing that the yellow plunger is completely depressed)?”

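### SAP 6.10 counts a dose injected on time but delivered incompletely as missed, and its two compliance measures end on different dates (minor: descriptive tables only)

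*SAP*

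**What the plan says.** SAP 6.10 defines two compliance summaries.

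- **Missed doses.** The derivation is "Date of last dose – Date of first dose +1 minus the ZLP-AI kits with complete dose delivery". Participants are then tabulated by number missed, starting with "Participants missing 1 dose" and ending with 4 or more. The SAP amendment log (6.14.1) explains that the formula was added because the discontinuation page of the eCRF cannot capture missed doses in participants who complete the study.
- **Percentage compliance**, presented as an additional evaluation. It is "number of used and returned ZLP-AIs with complete dose delivery / (Expected duration of use"), with the denominator "calculated as: (date of last scheduled visit / EW visit) - (date of first ZIL-AI use) +1".

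Other sections bear on these rules:

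- SAP 4.2.1 ties the delivery question to returned devices: "the investigator should answer the following eCRF question for each ZLP-AI used and returned throughout the Intervention Period".
- SAP 4.2.2 foresees lost, stolen or missing devices, and plans counts of devices dispensed, returned used and returned unused.
- SAP 4.2.3 counts the devices that should have been used from first to last self-administration, not up to a visit.
- SAP 4.1.1.5 ends the Intervention Period at the last on-site ZLP-AI application or the early withdrawal (EW) visit, and regards it as completed once Visit 8 on Day 14 has taken place.
- Protocol Table 1-1, footnote b, asks a withdrawing participant to "return to the clinic for an EW Visit as soon as possible but no later than the next scheduled in-clinic visit". Protocol 7.1 adds that stopping medication does not by itself remove a participant from the study.

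**The concern.** A missed dose and an incomplete delivery are different events. The first concerns the participant's adherence; the second may concern the device or how it was handled. The SAP separates them elsewhere: the PK exclusion rules in 4.4.3 list a missed dose and a dose below the full amount as distinct grounds. The missed-dose formula in 6.10 merges them, because it subtracts only complete deliveries from the days elapsed.

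The formula also stops at the last dose taken, so doses not taken after that date can never enter the count. The percentage runs on to a visit date. For a participant who stops early, the two lines of the compliance output can therefore point in opposite directions, and the SAP gives no reason for the different spans.

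What is at stake is the reading of the compliance tables. With about 25 participants, one misclassified person moves a category by 1/25 = 4 percentage points, and two by 8.

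**Working it through.** **Inputs.** Fourteen planned self-administrations, one per day, the last at Visit 8 on Day 14 (SAP 1.2; Protocol Table 1-1 and 6.1); at least 25 participants (SAP 5); the two formulas in SAP 6.10. Day 1 is first use throughout.

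**The plan's own figure.** 25 × 14 = 350, which matches the approximately 350 self-administrations in SAP 5. No compliance figure is stated.

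**Formulas.**

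- Missed = (last dose day − 1 + 1) − complete devices
- Compliance = complete returned devices / (last visit day − 1 + 1)

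**Participants who inject on all 14 days, last visit on Day 14**

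| Case | Doses not injected | Missed per SAP 6.10 | Compliance |
|---|---|---|---|
| All complete and returned | 0 | 14 − 14 = 0 | 14/14 = 100% |
| 1 incomplete delivery | 0 | 14 − 13 = 1 | 13/14 = 92.9% |
| 2 incomplete deliveries | 0 | 14 − 12 = 2 | 12/14 = 85.7% |
| 3 devices used but not returned | 0 | 14 − 11 = 3 (by inference) | 11/14 = 78.6% |

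In the last row the percentage falls by the explicit wording of its numerator, which requires return. The missed count does not mention return. It rises only because the delivery question is answered for returned devices (SAP 4.2.1), so an unreturned one would probably have no confirmed complete delivery.

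**Participant with 5 complete, returned doses on Days 1 to 5**

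| Last visit or EW visit | Missed per SAP 6.10 | Compliance |
|---|---|---|
| Day 6 | 5 − 5 = 0 | 5/6 = 83.3% |
| Day 8 | 0 | 5/8 = 62.5% |
| Day 10 | 0 | 5/10 = 50.0% |
| Day 12 | 0 | 5/12 = 41.7% |
| Day 14 | 0 | 5/14 = 35.7% |

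Day 14 is the latest EW date that footnote b allows, and also the Visit 8 date for someone who stops dosing and stays in the study.

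**With one span for both measures**, same participant, last visit on Day 14. Span to the visit: 14 − 5 = 9 missed and 5/14 = 35.7%. Span to the last dose: 5 − 5 = 0 missed and 5/5 = 100%. Either choice makes the two lines agree.

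**With used devices counted instead of complete ones**, the participants in the first table have 14 − 14 = 0 missed. The incomplete or unreturned devices appear on their own lines.

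**The case against.** The strongest reply is that little depends on this. Adherence is neither an objective nor an endpoint. SAP 4.2.2 and 4.5.4 already report used, unused, malfunctioning and unreturned devices, and listings will resolve odd cases in a study of this size. The percentage is labelled an additional evaluation, so two different measures may be intended: no gaps between first and last dose, and 5 of 14 doses delivered by Day 14, can both be true of someone who stops early. For a fully adherent completer the measures agree. All of this stands and sets the severity. It does not explain why an injected dose should be called missed, or why the end date of the percentage carries no visit number.

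Four stronger readings might be inferred, and the documents do not support them.

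- **An adherent completer scores 67%.** This takes Visit 9 as the last scheduled visit: 14/21 = 66.7%, or 14/24 = 58.3% to 14/18 = 77.8% across the follow-up window. SAP 4.1.1.5 does count phone calls among scheduled visits, so the wording is open. But the quantity being defined is the expected duration of use, and the same section ends the Intervention Period at the last on-site application or EW visit. Visit 8 is the natural reading.
- **36% is the typical gap.** It needs dosing to stop on Day 5 and a last visit on Day 14. The protocol asks for the EW visit as soon as possible, and a Day 6 visit gives 83%.
- **Unreturned devices are expressly counted as missed doses.** Only the percentage says so; for the count it is an inference.
- **The effectiveness results are affected.** SAP 4.2.2 and 4.3 use their own numerators and denominators and do not draw on 6.10.

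**Conclusion.** The point holds, at minor severity. Applied as written, the missed-dose rule overstates missed doses by one for each incomplete delivery between the first and last dose, and probably by one for each used device that is not returned. It cannot register doses not taken after the last one. The two measures end on different dates, so an early stopper can show 0 missed doses with compliance anywhere from 83% (EW visit on Day 6) to 36% (last visit on Day 14) after 5 doses.

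These figures assume one device per day, as Protocol 6.1 specifies, and Visit 8 as the last scheduled visit for completers. How many participants will be affected cannot be known from the documents; it depends on the number of incomplete deliveries, unreturned devices and early stops. The consequence is limited to the descriptive compliance tables.

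**What to change.** Amend SAP 6.10 as follows:

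1. Compute missed doses as expected dosing days minus the number of ZLP-AIs used, complete or not and returned or not, from the per-device administration page (SAP 4.2) and the accountability log (SAP 4.2.2).
2. Report incomplete deliveries and used but unreturned devices on separate lines.
3. Replace *last scheduled visit* with *Visit 8*.
4. State one span and use it for both the count and the percentage. Whether it ends at the EW visit or at the last dose for early stoppers is a choice of definition. If SAP 4.2.3 keeps a different span, say why.

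The data need checking first. The eCRF is not among the documents, and none of them confirms a dated record of each home injection. SAP 4.2 describes the administration page as recorded at Visits 1 and 8, and calls are scheduled on 6 of the 12 home days. Step 1 needs only a count of devices used, but it does require that an unreturned device can be identified as used. If that is not possible, keep the present derivation and relabel the count *missed or not confirmed complete*.

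The cost is a few lines of SAP text and reprogramming of the compliance table.

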6.11 Appendix 11: PK calculations

See Section 4.4.3.

6.12 Appendix 12: PK standard reporting procedures

See Section 4.4.3.

6.13 Appendix 13: Data transparency reporting

For results disclosure on public registries (eg, ClinicalTrials.gov), treatment-emergent adverse events and treatment-emergent serious adverse events will be published.

Mandatory outputs to disclose:

Tables:

- Disposition and Discontinuation Reasons
- Discontinuation due to AEs
- Demographics
- Incidence of TEAEs – Overview (including both All Deaths and TEAE leading to Deaths)
- Incidence of Non-Serious TEAEs Above Reporting Threshold of 5% of Participants
- Incidence of serious TEAEs by Relationship
- Incidence of fatal TEAEs by Relationship

Listings:

- Study Discontinuation

6.14 Appendix 14: Details on amendments to the statistical analysis plan

6.14.1 Amendment 1.0

The main purpose of the SAP amendment 1.0 was to make the following changes to the original SAP version dated 24 September 2024.

- Specific data of MG0011 within participants that rolled over from MG0011 into DV0013 will be included in the study outputs. Directions on how to handle these cases are provided.
- To facilitate the Plain Language Summaries (PLS)
- To add further clarity while programming the TFLs

All changes are listed in the below table. The table below does not include corrections of minor typographical errors and formatting/stylistic changes.

Table 6–7: Summary of Changes

Section # and Name	Description of Change	Brief Rationale
List of Abbreviation	PLS abbreviation added	New abbreviation
4.1.1.4 Handling of missing dates and times	Deleted text: In the event of ambiguity or incomplete data which makes it impossible to determine whether a medication/AE was concomitant/treatment emergent or not, the medications/AEs will be considered as concomitant/treatment emergent. Programming rules were added for the imputation of stop dates	Text is redundant as it already exists in the same paragraph (duplication) To add clarity on the programming
Section 4.1.1.6 MG0011 data	Section is added	As per protocol, only the medications taken during the DV0013 study entry are rolled over from the parent study MG0011 to DV0013. Any other important participant information that needs to be summarized within DV0013 outputs will be based on the MG0011 datasets.
Section 4.5.2.3 Adverse Events Summaries	Outputs are added to complete the list of PLS outputs	As requested by the Team
Section 4.5.3 Tolerability – Injections and Medication Errors	Following text has been deleted: Separate shift tables from Visit 1 to Visit 8 will assess participants' conception on the pain and skin reactions during or after the self-injection, based on a 5 level Likert type scale (Not at all bothered, ..., Extremely bothered). The assessments to be summarized include pain, burning sensation, cold sensation, Itching, redness, swelling, bruising and hardening.	The SIAQ Version 2.1 questionnaire is recorded in the MyVeeva platform. During the study, it was observed that a portion of it was also captured in the study eCRF, resulting in duplicate data. It has been decided to leave the eCRF blank for all subjects on the corresponding page to eliminate the redundancy. The deleted text from the SAP pertains to the redundant SIAQ.

Section # and Name	Description of Change	Brief Rationale
Section 4.5.5.2 Vital signs	Deleted text related to the summaries of the pulse rate based on the average of 3 readings.	Pulse rate is be assessed in triplicate readings.
Section 4.5.5.4 Columbia-Suicide Severity Rating Scale (C-SSRS)	Participants are assessed via different versions of C-SSRS depending on if they have previously completed the Screening/Baseline version or not.	DV0013 participants coming from MG0011 and were previously enrolled in MG0009 study have never been assessed for suicidal behavior with reference to lifetime. This is not the case for the MG0011 participants within DV0013 who were previously enrolled in MG0010.
Section 6.3.1 Baseline characteristics and demographics	Age categories are updated to: Age (<18, 18 - <65, 65 - <85 and ≥85 years	To reflect the most recent standard age group categories as per UCB guidance in the standard shells template.
Section 6.6 Appendix 6: Prior/concomitant/follow-up medications	Added Text related to the summaries of Neisseria Vaccination.	Medications stopped before 30 days prior first dose in DV0013 are not in scope for this study. Exception is the Neisseria vaccination history that a full record of vaccination is needed.
Section 6.6.1	Any medications captured will be summarized and listed in SS instead of ES	Participants not dosed are not in scope for past, prior, and concomitant medications.
Section 6.10 Appendix 10: Compliance	A formula for derivation of the number of missed doses is provided. Text related to the capturing of missed doses through the study medication discontinuation eCRF page is deleted.	The eCRF page of study medication discontinuation is applicable for participants who discontinue the study. Thus, the number of missed doses cannot be captured within study completers. Thus, a derivation of the number of missed doses is provided.

